1. STUDY SUMMARY

Sponsor Contact Information	Ohio Pain Clinic [name] [name]				
Study Purpose	The purpose of this study is to evaluate the effect of pulse widths <500 μ S and >1000 μ S on clinical outcomes during a temporary SCS trial.				
Study Design and Scope	The proposed study is a prospective, single-center, two arm, randomized, crossover design to be conducted at The Ohio Pain Clinic. The study will enroll up to 15 subjects in order to include up to 10 subjects in the study. Subjects selected to participate in the trial have back and/or leg pain, have been evaluated as a candidate for SCS and have agreed to undergo a temporary SCS trial using the Algostim system with percutaneous leads. Each subject will be followed during the trial period of approximately 7 days.				
	The study will end when the last subject has completed the trial period. exited. The expected enrollment period for this study is approximately three months. After exit from the clinical study, subjects will continue to be followed by their physician per usual care. All device and procedure-related AEs will be collected and reported per the study protocol.				
Primary Effectiveness Objective	Compare the change from baseline of pain scores between the two study arms. Pain scores are obtained using the Numeric Rating Score (NRS) administered at baseline and after completion of each arm of the study.				
Secondary	Secondary measures of therapy effectiveness will include:				
Effectiveness Objectives	Paresthesia distribution: At end of each arm, subjects will be asked to complete a diagram that shows distribution of paresthesia.				
	 At the end of the trial period, subjects will be asked to select their favorite program. 				
	 At the end of the trial period, subjects will be asked to rate the quality of the pain relief achieved during the trial (from either arm) using the following scale; Excellent, Very Good, Good, Fair or Poor. 				
	 At the end of the trial period, subjects will be asked to rate their overall satisfaction with the pain relief achieved during the trial (from either arm) using the following scale: Very Satisfied, Satisfied, Neither Satisfied nor Unsatisfied, Unsatisfied, or Very Unsatisfied. 				
	 Number of patients who achieved ≥ 50% pain relief during the trial (from either arm) 				
Secondary Safety	Secondary measures of therapy safety will include:				
Objectives	Rate of device-related and/or procedure-related AEs from the Trial procedure through study completion.				

Study Procedures

After the subject has consented to the study, he or she will be enrolled in the clinical study and undergo a baseline evaluation. The patient will then be randomly assigned to arm one (pulse with <500 μ S) or arm two (pulse width >1000 μ S) and undergo an Algovita trial procedures. Following the trial procedure, the subject's EPG will be set to the appropriate pulse width, based on the arm assigned, and then programmed to achieve optimal pain relief. For the next three days, the subject will evaluate pain relief generated by the 1st assigned program (arms).

After 3 days, the patient will visit the Ohio Pain Clinic for data collection and then reprogramming of the EPG for the next arm. For the next three days, the subject will evaluate the SCS therapy generated by the 2nd assigned program and then return to the clinic for data collection, removal of the leads and exit from the study. After the subject is exited from the study, he or she will be followed by the Ohio Pain Clinic per usual care. The data collection requirements are listed below.

Enrollment:

- Informed consent signed
- Confirmation of study eligibility

Baseline evaluation:

- Relevant medical history
- Physical examination
- Brief Pain Inventory
- Demographics
- Record pain ratings and pain map

After the lead implantation:

- Implant procedure
- Document SCS products & lead configuration, electrode position and programmed parameters

4 and 7 day (+/- 2) Post-Implantation:

- Record pain rating for current arm
- Record paresthesia and pain map for current arm
- Document AEs
- Program subject with next arm parameters and document

Study Exit

- Record pain rating for current arm
- Record paresthesia and pain map for current arm
- Record program preference
- Record satisfaction and pain relief from each program
- Document study exit reason & AEs

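### The ≥50% responder objective counts response in either arm, so it describes overall success of the temporary trial and cannot show whether response differs by pulse width

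*Protocol*

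**What the plan says.** All of the following is in the protocol's Study Summary unless another place is named.

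- **Purpose:** "The purpose of this study is to evaluate the effect of pulse widths <500 μ S and >1000 μ S on clinical outcomes".
- **Design:** a "prospective, single-center, two arm, randomized, crossover design", so each subject is meant to receive both pulse widths in turn.
- **Size:** "The study will enroll up to 15 subjects in order to include up to 10 subjects in the study".
- **Primary effectiveness objective:** "Compare the change from baseline of pain scores between the two study arms", using an NRS "administered at baseline and after completion of each arm of the study".
- **Responder objective (secondary):** "Number of patients who achieved ≥ 50% pain relief during the trial (from either arm".

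Two other secondary items, the rating of quality of relief and the rating of overall satisfaction, carry the same either-arm qualifier. The Study Exit list under Study Procedures works per program instead: "Record satisfaction and pain relief from each program". Table 6-1 repeats that per-program item. No responder count by pulse width is stated anywhere in the protocol.

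**The concern.** The study exists to learn what pulse width does, and it uses a crossover so that each subject can be compared with himself or herself. The responder objective merges the two periods: a subject who reaches 50% relief under one setting, the other, or both adds one to the same total. Once merged, the total cannot be separated by pulse width.

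Two things follow. The count gives no information on whether response differs between the settings. It also gives each subject two opportunities to qualify, so it tends to sit above the response rate of either setting taken alone. A reader who took it as the yield of one pulse width would usually be reading too high a figure.

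**Working it through.** **Plan's own figure.** There is none to reproduce. The protocol states no expected responder rate and no within-subject correlation. The rates and correlations below are assumptions; n = 10 is the protocol's maximum number of included subjects.

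**Step 1: does the count contain a contrast between arms?** Let A be the set of responders under <500 μS (narrow) and B the set under >1000 μS (wide). The protocol counts A ∪ B. Suppose the result is 7 of 10. That fits:

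- 7 narrow and 0 wide;
- 7 narrow and 7 wide, the same subjects;
- 4 narrow and 3 wide, different subjects (4 + 3 = 7).

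The same holds for rates. With independent responses, a 75% either-arm rate arises from 50%/50% (1 − 0.5 × 0.5), from 60%/37.5% (1 − 0.4 × 0.625) and from 75%/0%. The count therefore cannot tell equal arms from very unequal ones.

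**Step 2: where does the count sit relative to each arm?** Since |A ∪ B| = |A| + |B| − |A ∩ B| and |A ∩ B| ≤ min(|A|, |B|), the union is at least max(|A|, |B|). Equality holds only when every responder in the arm with fewer responders also responds in the other arm. Ties are possible, so the correct statement is at least as high, and not always higher.

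**Step 3: size of the excess.** P(either) = p₁ + p₂ − P(both), with P(both) taken from a bivariate normal with latent within-subject correlation r. For p₁ = p₂ = 0.5 this is P(both) = 1/4 + arcsin(r)/(2π). At r = 0.5, P(both) = 0.25 + 0.0833 = 0.333 and P(either) = 1 − 0.333 = 0.667, which is 6.7 of 10.

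Expected either-arm count, n = 10:

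| Assumed response, narrow / wide | Per-arm expected count | r = 0 | r = 0.5 | r = 0.7 | r = 0.9 |
|---|---|---|---|---|---|
| 30% / 30% | 3.0 each | 5.1 | 4.4 | 4.1 | 3.6 |
| 50% / 50% | 5.0 each | 7.5 | 6.7 | 6.3 | 5.7 |
| 70% / 70% | 7.0 each | 9.1 | 8.4 | 8.1 | 7.6 |
| 40% / 60% | 4.0 and 6.0 | 7.6 | 6.8 | 6.5 | 6.1 |

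At 50% per arm the excess runs from 0.7 subject (r = 0.9) to 2.5 subjects (r = 0).

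**Cross-check with another correlation model.** Let φ be the correlation between the two yes/no outcomes, so that P(both) = p² + φp(1 − p). At p = 0.5 and φ = 0.5, P(both) = 0.25 + 0.125 = 0.375 and P(either) = 0.625. This is close to the 0.627 given by the latent model at r = 0.7.

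**Step 4: how often is the observed count strictly above both arms?** This needs at least one narrow-only and one wide-only responder. With discordant probabilities b = p₁ − P(both) and c = p₂ − P(both), the probability is 1 − (1 − b)ⁿ − (1 − c)ⁿ + (1 − b − c)ⁿ. At 50% per arm and n = 10 it is 0.89 (r = 0), 0.69 (r = 0.5), 0.54 (r = 0.7) and 0.26 (r = 0.9).

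**Step 5: are the data for a per-arm count planned?** Yes. The primary objective already needs the baseline NRS and the NRS after each arm, and the exit visit also records relief for each program.

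**The case against.** The strongest reply is that this endpoint never claims to compare pulse widths. It is secondary, it says openly that relief may come from either arm, and two neighbouring items use the same qualifier. It reads naturally as a deliberate description of how the temporary trial went overall. That reading is plausible, and it is why the point is a limited one. The effect on the endpoint is unchanged: the only responder measure in a pulse-width study gives no result by pulse width.

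Second, the study question is addressed elsewhere. The primary objective compares pain scores between arms, the favorite-program choice is a within-subject comparison, and paresthesia is mapped at the end of each arm. This stands. A reader might infer that the crossover's within-subject contrast is thrown away for the study as a whole; the protocol does not support that.

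Third, the excess depends on assumed inputs. Both ratings come from the same subject, with the same leads, about three days apart, so independence is an extreme case and the 7.5 of 10 is the top of the range. This also stands, and the range should be read down to small excesses.

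Fourth, a per-arm test would have little power. An exact McNemar test at two-sided 5% needs at least six discordant subjects, all in one direction: 6–0 gives 2 × (1/2)⁶ = 0.031, while 5–0 gives 0.0625. True, and it is a reason to present the paired table descriptively, not a reason to omit it.

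Fifth, the protocol does not say whether ≥50% relief is derived from the NRS or from the relief recorded per program at exit, and an SAP might settle this or add per-arm counts. That may be so, but the objective as the protocol words it would remain the either-arm count.

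**Conclusion.** The point holds in limited form. As written, the responder objective describes overall success of the temporary trial and cannot show whether response differs by pulse width. That conclusion needs no assumption; it follows from counting a union.

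The count is never below the larger per-arm count and is in expectation higher unless responders are fully nested. The size of the excess does rest on assumptions: at 50% per arm and n = 10, it is about 0.7 to 2.5 subjects for latent correlation 0.9 to 0. A reader might infer that the count must exceed what either pulse width delivers. It need not: at r = 0.9 it would be strictly above both arms only about 26% of the time.

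The loss is confined to one secondary endpoint and can be recovered from data already planned. It deserves correction, but it does not threaten the primary comparison.

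**What to change.** - Define the responder endpoint as a reduction of at least 50% from the baseline NRS at the end of each arm.
- Report the number of responders separately for <500 μS and >1000 μS.
- Add the paired 2x2 table: both, narrow only, wide only, neither. Present it as descriptive, given at most 10 subjects.
- If the either-arm count is kept, label it as a description of overall trial success and not as a pulse-width result.

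The cost is one sentence in the secondary objectives and one table. No visit, instrument or data item is added.

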1.1 OVERVIEW OF DATA COLLECTION AT STUDY VISITS

Enrolled subjects will have up to 5 scheduled visits as follows: Enrollment, Baseline, Implant, Follow-up at 4 and 7 days (+/-2) post implantation and a Study Exit visit as shown in Table 6.1.

Assessments and Data Collection	Enrollment	Baseline	After Implant	Follow-up Visits	Study Exit
Eligibility confirmation	✓				
Medical historyPhysical exam	✓				
Informed Consent	✓				
Record demographicsBrief Pain InventoryRecord pain map		✓			
Implant and System information			1		
 Record pain rating for current arm Record paresthesia and pain map for current arm Document any AEs 				1	1
 Record subject program preference Record subject satisfaction and pain relief from each program Document study exit reason & any AEs 					1

Table 6-1: Summary of Assessments at Each Visit

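### The day-4 and day-7 visit windows overlap and are both counted from implantation, so the two pulse widths can be rated after very unequal exposure

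*Protocol*

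**What the plan says.** The Study Procedures narrative in the Protocol's Study Summary gives three days on the first assigned program, then a clinic visit for data collection and reprogramming. Of the second period it says: "For the next three days, the subject will evaluate the SCS therapy generated by the 2nd assigned program". The subject is then to "return to the clinic for data collection, removal of the leads and exit from the study".

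The visit list in the same section puts the post-implant visits at "4 and 7 day (+/- 2) Post-Implantation". Section 1.1 repeats this as "Follow-up at 4 and 7 days (+/-2) post implantation and a Study Exit visit". In both places the days are counted from implantation and the tolerance follows the pair of days.

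The list under that heading includes "Program subject with next arm parameters and document", with nothing to limit it to the first of the two visits. Study Exit has its own list but no day or window. Section 1.1 opens with "Enrolled subjects will have up to 5 scheduled visits as follows" and then names six: enrollment, baseline, implant, two follow-ups and exit.

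The primary effectiveness objective compares change in the Numeric Rating Score between arms, with the score "administered at baseline and after completion of each arm of the study".

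**The concern.** In a crossover, each subject's difference between the two end-of-arm ratings should isolate the treatment, here pulse width. That requires the two ratings to follow similar time on program. A tolerance of ±2 days is two-thirds of a three-day treatment period, and with both windows anchored to implantation a late first visit shortens the second arm day for day unless the second visit is also moved.

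If one pulse width is rated after 6 days and the other after 1, the subject's difference mixes pulse width with time on therapy, recovery from the lead procedure and, since no washout is stated, carryover from the first program. Paresthesia maps and program preference rest on the same exposure. The study includes up to 10 subjects, so a few uneven schedules could matter.

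**Working it through.** **Inputs.** Nominal days 4 and 7, each ±2, from implantation (Study Summary visit list; section 1.1). Intended exposure of three days per arm (Study Procedures narrative). Trial period of about 7 days (Study Design). Let A be the day of the first follow-up visit and B the day of the second, with B taken as the end of arm two.

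**The plan's own figure.** At nominal days the second arm lasts B − A = 7 − 4 = 3 days, as the narrative says. The first arm lasts 4 days if implantation is day 0, or 3 days if it is day 1. The nominal days are therefore compatible with the narrative, and the difficulty is the tolerance.

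**Windows.** A: 4 ± 2 = days 2 to 6. B: 7 ± 2 = days 5 to 9. Overlap: days 5 and 6.

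**Second-arm length, B − A.**
- Longest: 9 − 2 = 7 days.
- Shortest: 5 − 6 = −1, which is impossible in sequence, so 0 days (both visits on day 5 or both on day 6).

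This range is the same under either day numbering.

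**Exposure under each numbering.**

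| | Implant = day 0 | Implant = day 1 |
|---|---|---|
| First-arm length | A: 2 to 6 days | A − 1: 1 to 5 days |
| Second-arm length | 0 to 7 days | 0 to 7 days |
| First minus second, maximum | 6 − 0 = +6 | 5 − 0 = +5 |
| First minus second, minimum | 2 − 7 = −5 | 1 − 7 = −6 |
| Feasible pairs: second arm longer / equal / shorter | 9 / 2 / 13 | 11 / 3 / 10 |

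There are 5 × 5 = 25 whole-day pairs. One (A = 6, B = 5) is impossible, leaving 24. Only 5 of them, (2,5), (3,6), (4,7), (5,8) and (6,9), give a three-day second arm. These counts show what the windows tolerate; they do not predict how the clinic will schedule.

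**One off-target visit is enough.** With the second visit on time at day 7 and implantation as day 0:

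| First visit | First arm (days) | Second arm (days) |
|---|---|---|
| Day 2 | 2 | 5 |
| Day 3 | 3 | 4 |
| Day 4 | 4 | 3 |
| Day 5 | 5 | 2 |
| Day 6 | 6 | 1 |

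With implantation as day 1, the first-arm figures each fall by one (1 v 5 up to 5 v 1). With the first visit on time at day 4, the second arm runs from 5 − 4 = 1 to 9 − 4 = 5 days.

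**Alternatives checked.**
- ±2 applied to day 7 only: no overlap, but the second arm still runs 1 to 5 days.
- ±1 on both visits, still counted from implantation: windows 3-5 and 6-8, no overlap, second arm 6 − 5 = 1 to 8 − 3 = 5 days. Narrowing alone does not solve it.
- First visit 3±1 days from implantation and second 3±1 days from reprogramming: 2 to 4 days per arm, largest difference 4 − 2 = 2 days, total 2 + 2 = 4 to 4 + 4 = 8 days.

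**The case against.** The strongest reply is that the narrative already times the second arm from reprogramming. Read that way, the windows move together: first visits on days 2, 3, 4, 5 and 6 plus three days give second visits on days 5, 6, 7, 8 and 9, exactly the day-7 window. The second arm then stays at 3 days and only the first varies, so the largest within-subject difference is 6 − 3 = 3 days (implantation as day 0) or 2 days (implantation as day 1). The latter equals the maximum under the proposed fix.

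This is a possible reading and probably the intention. But no text ties the second window to reprogramming, and a coordinator who schedules 6 days against 1 stays within both stated windows. Even on this reading the first arm varies over 2-6 (or 1-5) days against a fixed three.

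It can also be said that day 7 need not end arm two, since Study Exit is listed separately. The narrative's single return visit and the five-visit maximum favor day 7. If exit is a separate visit, the 0-7 range does not apply, but then the end of arm two has no stated day at all.

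Two further points stand. Procedural recovery, period effects and carryover would exist with exact 3+3 timing too; unequal exposure adds to them but does not create them. And nothing in the protocol shows how pain scores differ by days of stimulation, so the added noise cannot be quantified.

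**Conclusion.** The concern holds and should be fixed. As written, the windows tolerate 0 to 7 days on the second program against an intended three, and a within-subject difference in exposure of up to 6 days in either direction, depending on day numbering. These are limits, not expected values.

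The conclusion assumes that ±2 applies to both visits, that day 7 ends the second arm, and that no timing rule sits in material not shown, such as the design figure. The consequence is extra noise and added period and carryover effects in the primary comparison, with possible chance imbalance in exposure between pulse widths in so small a sample. Randomized order protects against a systematic advantage for either pulse width, but it does not equalize exposure within a subject.

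**What to change.** In the Study Summary visit list and section 1.1:

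- Set the first end-of-arm visit at 3±1 days after implantation and the second at 3±1 days after reprogramming. The 4 to 8 days in total fit the stated trial period of about 7 days.
- State that the second end-of-arm visit is the Study Exit visit, which also reconciles the six named visits with the maximum of five.
- List reprogramming at the first visit only.
- Record actual days on each program on the CRF, if the draft forms (in an appendix not available here) do not already do so.

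These are wording changes. They need no extra visits or subjects, and the only cost is slightly less scheduling flexibility.

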1. STUDY DESIGN

The proposed study is a prospective, single-center, two arm, randomized, crossover design to be conducted at The Ohio Pain Clinic. The study will enroll up to 15 subjects in order to include up to 10 subjects in the study. Subjects selected to participate in the trial have back and/or leg pain, have been identified as a candidate for SCS and have agreed to undergo a temporary SCS trial using the Algostim system with percutaneous leads. Each subject will be followed during the trial period of approximately 7 days.

The study will end when the last subject has completed the trial period or is exited. The expected enrollment period for this study is approximately three months. After exit from the clinical study, subjects will continue to be followed by their physician per usual care. All device and procedure-related AEs will be collected and reported per the study protocol.

[figure not shown]

Figure 6-1: Algovita SCS Post-Market Clinical Study Design

1.1 OVERVIEW OF DATA COLLECTION AT STUDY VISITS

Enrolled subjects will have up to 5 scheduled visits as follows: Enrollment, Baseline, Implant, Follow-up at 4 and 7 days (+/-2) post implantation and a Study Exit visit as shown in Table 6.1.

Assessments and Data Collection	Enrollment	Baseline	After Implant	Follow-up Visits	Study Exit
Eligibility confirmation	✓				
Medical historyPhysical exam	✓				
Informed Consent	✓				
Record demographicsBrief Pain InventoryRecord pain map		✓			
Implant and System information			1		
 Record pain rating for current arm Record paresthesia and pain map for current arm Document any AEs 				1	1
 Record subject program preference Record subject satisfaction and pain relief from each program Document study exit reason & any AEs 					1

Table 6-1: Summary of Assessments at Each Visit

2. STUDY PROCEDURES

2.1 DATA COLLECTION REQUIREMENTS

Subject data will be collected and documented on case report forms (CRFs). Drafts of the CRFs for this study are located in Appendix 17.

2.1.1 Subject Screening Procedure

Subjects will be screened from candidates for SCS, that have agreed to undergo an SCS temporary trial and that meet study eligibility. Subjects who meet this criteria will be asked to participate in the study and if they agree will be required to sign an informed consent prior to any study-related procedures or data collection occurring.

Assessments and Data Collection	Enrollment	Baseline	After Implant	Follow-up Visits	Study Exit
 Eligibility 	✓				
Medical history	1				
Physical exam					

•	Informed Consent	✓				
•	Record demographics		✓			
•	Brief Pain Inventory					
•	Record pain map					
•	Implant and System information			✓		
•	Record pain rating for current arm				1	1
•	Record paresthesia and pain map for					
	current arm					
•	Document any AEs					
•	Record subject program preference					1
•	Record subject satisfaction and pain					
	relief from each program					
•	Document study exit reason & any AEs					

Table 6-1: Summary of Assessments at Each Visit
